#### 3.1 Eligibility Criteria

\_\_\_\_\_ 3.1.1 Estrogen receptor (ER) and/or progesterone receptor (PR) positive histologically confirmed adenocarcinoma of the breast with staining of  $\geq 1\%$  cells will be considered positive. Receptor status may be based on any time during treatment prior to study randomization, and from any site (i.e. primary, recurrent, or metastatic).

\_\_\_\_\_ 3.1.2 Patients whose tumors have HER2 IHC 3+, ISH  $\geq 2.0$ , or average HER2 copy number  $\geq 6.0$  signals per cell are not eligible. Receptor status may be based on any time during treatment prior to study randomization, and from any site (i.e. primary, recurrent, or metastatic).

\_\_\_\_\_ 3.1.3 Patients must have measurable or non-measurable Stage III/locally advanced or metastatic carcinoma of the breast, as defined in Section [6.1.2](#), where local therapy with curative intent is not possible. Lesions must be evaluated  $\leq 4$  weeks prior to study randomization. Diagnostic-quality CT scans with both oral and IV contrast are the expected radiologic method, unless an alternative is approved per Section [6.1.3](#).

**NOTE:** Where baseline imaging has already been performed  $\leq 6$  weeks prior to study randomization, repeat imaging may not be required. Please refer to footnotes 5 and 6 of Study Calendar (Section [7](#)).

**NOTE:** As of October 16, 2016, accrual of new patients having non-measurable disease has stopped. Per Section [9.2](#), the planned accrual for this target population has been reached.

Rev. Add5

Rev.10/15

- \_\_\_\_\_ 3.1.4 Pre/peri- and postmenopausal women and all men are eligible for this trial. Postmenopausal is defined as:
- Age  $\geq$  55 years and one year or more of amenorrhea.
  - Age  $<$  55 years and one year or more of amenorrhea, with estradiol  $<$  20 pg/ml.
  - Age  $<$  55 with prior hysterectomy but intact ovaries, with estradiol  $<$  20 pg/ml.
  - Prior bilateral oophorectomy.

**NOTE:** Women who do not fit the criteria for being postmenopausal as above are deemed pre- or peri-menopausal. Pre/perimenopausal women and all men can enroll provided they agree to receive concomitant LHRH agonist. Pre/perimenopausal women must have commenced treatment with LHRH agonist at least 4 weeks prior to randomization. If patients have received alternative LHRH agonist prior to study entry, they must switch to goserelin for the duration of the trial.

Rev.10/15

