- \_\_\_\_\_ 3.1.5 Sexually active males and pre/perimenopausal women must agree to use an accepted and effective method of contraception or to abstain from sexual intercourse for the duration of their participation in the study and for 3 months after discontinuation of therapy.

Rev.10/15

- \_\_\_\_\_ 3.1.6 Women must not be pregnant or breast-feeding.
- All females of childbearing potential must have a blood test or urine study  $\leq$  2 weeks prior to randomization.
- A female of childbearing potential is any woman, regardless of sexual orientation or whether they have undergone tubal ligation, who meets the following criteria: 1) has not undergone a hysterectomy or bilateral oophorectomy; or 2) has not been naturally postmenopausal for at least 24 consecutive months (i.e., has had menses at any time in the preceding 24 consecutive months).

Female? \_\_\_\_\_ (Yes or No)

Date of blood test or urine study: \_\_\_\_\_

- \_\_\_\_\_ 3.1.7 Patients must not have known central nervous system metastasis or a history of CNS metastases. Patients with leptomeningeal disease are not eligible.

- \_\_\_\_\_ 3.1.8 Patients must be disease-free of prior invasive malignancies for  $>$  5 years with the exception of curatively-treated basal cell or squamous cell carcinoma of the skin or carcinoma in situ of the cervix.

**NOTE:** If there is a history of prior malignancy, patients must not be receiving other specific treatment for that cancer.

Rev. 4/15

- \_\_\_\_\_ 3.1.9 Patients must meet at least one of the following criteria:
- \_\_\_\_\_ 3.1.9.1 Disease progression any time after non-steroidal AI use in the advanced disease setting.

Rev. 10/15  
Rev. 10/16

3.1.9.2 Relapse while on or within  $\leq 12$  months of end of adjuvant non-steroidal AI therapy with or without prior endocrine therapy for advanced disease.

**NOTE:** In either setting, treatment with any prior endocrine therapy must be completed  $\geq 2$  weeks prior to C1D1 of study treatment with the exception of exemestane which is permitted in the advanced disease setting within  $\leq 4$  weeks immediately prior to C1D1. Prior adjuvant exemestane is allowed if the disease free interval is  $>12$  months from the discontinuation of exemestane. Prior faslodex, everolimus, palbociclib or other CDK inhibitor (e.g. ribociclib, abemaciclib) use are allowed and must have been completed  $\geq 2$  weeks prior to C1D1. Failure to adhere to this washout guideline will result in a protocol violation.

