## 7. Study Parameters

1. Baseline evaluations within 4 weeks prior to randomization unless specified.
2. Prestudy scans and x-rays used to assess all measurable or non-measurable sites of disease must be done  $\leq$  4 weeks prior to randomization.
3. Prestudy CBC (with differential and platelet count) and all required prestudy chemistries must be done  $\leq$  4 weeks before randomization, as outlined in Section [3](#).

	Baseline	Cycle 1 Day 15	End of Cycles 1 and 2	End of Cycle 3	End of each cycle (cycle 3-forward) 	Every 3 cycles (cycle 3, 6 etc)	At discontinuation of treatment 	Post treatment 
History, Physical Exam, ECOG PS, Vital signs, Height, Weight	X 		X	X	X		X	X
Symptom/Toxicity assessments	X 		X	X	X		X	
CBC 	X	X	X	X	X		X	
Chemistries 	X	X	X	X		X	X	
Serum estradiol 	X							
ECG	X							
Bone scan 	X			X		X		X 
Tumor assessment by CT or MRI 	X			X		X	X	X 
Serum or Urine Pregnancy Test 	X							
PRO Assessments 	X			X		X	X	X
PRO Assessment: FBSI 	X		X	X	X			
PRO-CTCAE 	X		X	X	X		X	
Exemestane 				X (daily)				
Entinostat/placebo 				X (weekly)				
LHRH agonist (pre/perimenopausal female and all male participants only) 				X (monthly)				
Pill Count/Diary 			X	X	X	X	X	
Concomitant Medications	X		X	X	X		X	X 
Biological Sample Submissions [See Sections 11 and 12 ]								
Whole blood, one (1) 8mL CPT citrate tube 	X	X						

	Baseline	Cycle 1 Day 15	End of Cycles 1 and 2	End of Cycle 3	End of each cycle (cycle 3-forward) 	Every 3 cycles (cycle 3, 6 etc)	At discontinuation of treatment 	Post treatment 
FFPE tumor tissue (primary & metastatic) 	X							
Whole blood, one (1) 8mL ACD yellow top 	X							

	Cycle 1, Day 1 [2 samples drawn at least 2 hours apart, 2-5 hours after dosing]	Cycle 1, Day 15 [1 sample drawn 1 hour after dosing]	Within 72 hours prior to the start of Cycle 2
Population Pharmacokinetics [OPTIONAL PER PATIENT CONSENT]: Plasma, one (1) 6mL K2EDTA lavender top tube per time point 	X	X	X

- Physical exam, ECOG PS, vital signs, and symptom/toxicity assessment must be performed ≤ 2 weeks before randomization.  

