**NOTE:** Height measurements may have been taken > 4 weeks from baseline.
- CBCs, which includes WBC, ANC, Platelets, Hgb, and Hct required for protocol therapy must be done ≤ 72 hours prior to Cycle 2 and every cycle thereafter. Baseline CBCs do not need to be repeated prior to Cycle 1 Day 1.
- Albumin, alkaline phosphatase, total bilirubin, bicarbonate, BUN, calcium, chloride, creatinine, glucose, magnesium, phosphorus, potassium, total protein, SGOT (AST), SGPT (ALT), sodium must be done ≤ 72 hours prior to Cycles 2-4 and every 3 cycles thereafter. Baseline chemistries do not need to be repeated prior to Cycle 1 Day 1.
- Only required for women age < 55 years and with intact ovaries as described in Section [3.1](#).
- Baseline bone scan required in all patients.  
**NOTE:** If bone scan done ≤ 6 weeks prior to registration showed no evidence suggesting bone metastases and no clinical indication of skeletal pain or other evidence suggesting bone metastases, a repeat baseline bone scan is not required.
- CT of the chest and CT or MRI of abdomen/pelvis are required at baseline. Subsequent imaging for the subject should be conducted on the same scanner using the same acquisition and reconstruction parameters. Those tests required to follow known site(s) of disease must be repeated at the end of 12 weeks from randomization and then every 12 weeks (3 cycles) during treatment and according to the follow up schedule if off treatment, until first progression of disease. **NOTE:** All tumor assessment should be scheduled based on calendar time (every 12 weeks) and not cycle length. Image thickness (reconstructed) should be 5 mm or less for CT and MRI, and contiguous slices are preferred to those with intervening gaps. Consistent use of contrast agent, dose, and injection parameters (including time of image collection after contrast) are recommended. See Section [10](#) for additional details and submission instructions.  
**NOTE:** If the CT of the chest and CT or MRI of abdomen/pelvis done ≤ 6 weeks prior to randomization showed no evidence of disease in the area(s) and no clinical indication suggesting new metastases, full re-staging including all areas is not required; however, ensure that disease is evaluable per RECIST 1.1 requirements (Section [6](#)).
- Patient-Reported Outcomes to be assessed at the following time (see Section [5.6](#) for detailed instructions):

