13. Submit blood samples to the [name] Laboratory from patients who answer "Yes" to "I agree to participate in the laboratory research studies that are being done as part of this clinical trial." Baseline blood samples should be collected after randomization, prior to start of treatment on Day 1 (preferably within 2 days of Day 1). Day 15 blood samples should be collected prior to entinostat/placebo dose on that day.  
**NOTE:** Do not start treatment on Fridays as the baseline and day 15 blood collections cannot be shipped on Fridays.  
Submit optional blood and tissue samples for future research to the ECOG-ACRIN Central Biorepository and Pathology Facility (CBPF) from patients who answer "Yes" to "I agree to provide additional specimens for research."
- Rev. 10/16 14. All specimens submitted must be entered and tracked via the online ECOG-ACRIN Sample Tracking System (STS). The exact date and time of entinostat/placebo administration and of PK plasma sample collection must be entered into the STS.
- Rev. 10/16 15. Kits are available for blood collection and shipment. Kit order instructions are provided in Appendix VI. Kit orders will, on average, be delivered within 3 business days from time of order placement.
16. PRO-CTCAE items will be administered at Baseline, end of each Cycle, and at end of protocol treatment, including treatment discontinuation following the same schedule as trial Symptom/Toxicity assessments.
17. Concomitant Medications will be collected up to 90 days from the end of study treatment.
18. A complete cycle of treatment is defined as 28 days ( $\pm 3$  days) of once daily continuous treatment of exemestane in combination with entinostat/placebo. A new cycle start is defined as the first planned date of entinostat/placebo for the cycle.

Rev. 10/16  
Rev. 9/17

19. Pre/perimenopausal females must have commenced treatment with LHRH agonist at least 4 weeks prior to randomization. If patients have received alternative LHRHR agonist prior to study entry, they must switch to goserelin for the duration of the trial.
20. For all women of child bearing potential, must be done  $\leq$  2 weeks prior to randomization.

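### Sections 3.1.5 and 3.1.6 sort women by different menopause rules, so some are pregnancy-tested as of childbearing potential without being clearly asked for contraception

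*Combined protocol and SAP*

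**What the plan says.** Section 3.1.4 treats a woman as postmenopausal after a year of amenorrhea if she is 55 or over. If she is under 55 it requires "one year or more of amenorrhea, with estradiol" below 20 pg/ml. Two surgical routes are added: age under 55 "with prior hysterectomy but intact ovaries" and the same estradiol limit, or bilateral oophorectomy. The rest follow by default: "Women who do not fit the criteria for being postmenopausal as above are deemed pre- or peri-menopausal".

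Section 3.1.5 sets the contraception criterion: "Sexually active males and pre/perimenopausal women must agree to use an accepted and effective method of contraception", or else abstain, while on study and for 3 months after stopping therapy. Postmenopausal women are not mentioned.

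Section 3.1.6 requires a pregnancy test within 2 weeks before randomization for females of childbearing potential. It defines these as any woman who 1) "has not undergone a hysterectomy or bilateral oophorectomy; or 2) has not been naturally postmenopausal for at least 24 consecutive months", and explains limb 2 as menses within the past 24 months.

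In Section 7 the row "Serum or Urine Pregnancy Test" is marked at baseline only. Footnote 20 reads "For all women of child bearing potential, must be done" in the same 2-week window.

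Section 8.1.12 says entinostat must not be used in pregnancy. It expects women and men in entinostat studies to agree to acceptable contraception during treatment and for 3 months afterwards, with a qualifying phrase that refers to the study protocol.

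**The concern.** Two adjacent checklist items answer nearly the same question by different rules. Section 3.1.6 regards certain women as able to become pregnant and tests them. Section 3.1.5 leaves the same women out because 3.1.4 has already called them postmenopausal.

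Sites enroll from the Section 3 checklist. For these women the checklist asks for a baseline test but not for the agreement meant to prevent pregnancy afterwards. No later pregnancy test is scheduled for anyone, so after baseline prevention rests on that agreement. Pre/perimenopausal women must also take an LHRH agonist under 3.1.4, whereas women classed as postmenopausal need not. What is at stake is the consistency of a safety precaution for a drug that the protocol bars in pregnancy.

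**Working it through.** The plan gives no figure to reproduce, so the check applies the rules side by side. It is confined to women with uterus and ovaries intact and natural amenorrhea. Section 3.1.4 gives no cause for amenorrhea while 3.1.6 refers to natural menopause, so induced amenorrhea is left aside.

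The two limbs of 3.1.6 are joined by 'or'. Both readings are shown: limbs joined by 'and' (the likely intention) and the literal 'or'.

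| Months since menses | Age and estradiol (pg/ml) | Class in 3.1.4 | Named in 3.1.5 | Tested, 'and' | Tested, literal 'or' |
|---|---|---|---|---|---|
| <12 | any | pre/peri | yes | yes | yes |
| 12 to <24 | ≥55 | post | **no** | **yes** | **yes** |
| 12 to <24 | <55, estradiol <20 | post | **no** | **yes** | **yes** |
| 12 to <24 | <55, estradiol ≥20 | pre/peri | yes | yes | yes |
| ≥24 | ≥55, or <55 with estradiol <20 | post | **no** | no | **yes** |
| ≥24 | <55, estradiol ≥20 | pre/peri | yes | no | yes |

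1. Rows 2 and 3 are tested but unnamed under both readings. This part of the finding does not depend on interpretation.
2. Row 4 shows that the gap is conditional: under 55 with estradiol of 20 or more, she is still named.
3. Row 5 is tested but unnamed only under the literal 'or', because limb 1 alone is met by every woman who has had neither operation. There is then no upper limit on time since menses. Under 'and', the mismatch spans 24 − 12 = 12 months.
4. Row 6 is a mismatch in the other direction, under 'and' only: named but not tested. A redraft should close this too.

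As a count of logical profiles (not patients), intact women fall into 3 menses bands × 2 age groups × 2 estradiol levels = 12. In each band at or beyond 12 months, 3 of the 4 profiles are postmenopausal. Tested but unnamed: 3 profiles under 'and' (one band), and 3 × 2 = 6 under the literal 'or' (two bands).

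**The case against.** **Section 8.1.12 may already cover her.** Its subject is women and men without restriction, and the reference to the protocol follows directly after the word for methods. It can fairly be read as requiring contraception of everyone and leaving only the choice of method to the protocol. It can equally be read as pointing back to 3.1.5. A reader might infer that the protocol asks nothing of these women. The documents do not support that; they support only that coverage is unclear.

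**Two thresholds can be deliberate.** A single test is cheap and can cast a wide net, while months of contraception or abstinence justify a narrower one. Nothing in the protocol says the groups must match. This stands as a possibility, but the protocol does not state such a rationale. The literal 'or' also points to drafting: limb 1 alone captures every woman with uterus and ovaries, so limb 2 adds only women who have had one of the operations.

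**The group is small and at low risk.** Section 3.1.9 requires progression or relapse after a non-steroidal aromatase inhibitor, and Section 1.2.1 describes these drugs as acting in women whose ovaries no longer make estrogen. Few such women will have menstruated naturally within 24 months. The baseline test applies to them, and Section 5.2.7 requires pregnancies to be reported within 24 hours whatever the patient's age. All of this stands and limits the weight of the point.

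**A length of unprotected exposure.** A reader might add the 3 months after treatment to the planning median PFS in Section 9.2.1 and present the sum as an untested period peculiar to this group. It is not: women already named in 3.1.5 also have one scheduled test.

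**Conclusion.** The mismatch is real and minor. Women with uterus and ovaries intact, last natural menses 12 to under 24 months ago, and aged 55 or over (or under 55 with estradiol below 20 pg/ml) are tested as of childbearing potential but not named in the contraception criterion. This is true under either reading of 3.1.6. A reader might infer that the gap is exactly 12 months wide. That holds only if the limbs are joined by 'and'; the literal text leaves women at 24 months or more in the same position.

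The number of women affected is not in the documents. Endpoints, sample size, power and analyses are untouched. The conclusion rests on the visible text: the consent pages were removed and the adverse-event list for entinostat (Section 5.3) is redacted, so any contraception wording there could not be checked.

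**What to change.** Make two wording changes.

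- **3.1.5:** add a third group to the two already named, namely females of childbearing potential as defined in 3.1.6.
- **3.1.6:** define a female of childbearing potential as a woman who has had neither hysterectomy nor bilateral oophorectomy **and** who either has menstruated in the past 24 months or is pre/perimenopausal under 3.1.4.

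Against the table, rows 1 to 4 and row 6 become both tested and named, and row 5 becomes neither. Footnote 20 needs no edit because it already ties the test to childbearing potential. One harmless difference remains: a woman without a uterus who is deemed pre/perimenopausal (for example under 55, ovaries intact, estradiol 20 pg/ml or more) is named in 3.1.5 but not tested.

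No new data are needed. Menstrual history already drives both rules, and Section 7, footnote 4, already sets baseline estradiol: "Only required for women age < 55 years and with intact ovaries". The cost is a contraception-or-abstinence agreement for a small group at low risk of pregnancy.

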#### 4. Randomization Procedures

##### CTEP Registration Procedures

Food and Drug Administration (FDA) regulations and National Cancer Institute (NCI) policy require all individuals contributing to NCI-sponsored trials to register and to renew their registration annually. To register, all individuals must obtain a Cancer Therapy Evaluation Program (CTEP) Identity and Access Management (IAM) account (<https://ctepcore.nci.nih.gov/iam>). In addition, persons with a registration type of Investigator (IVR), Non-Physician Investigator (NPIVR), or Associate Plus (AP) (i.e., clinical site staff requiring write access to OPEN, RAVE, or TRIAD or acting as a primary site contact) must complete their annual registration using CTEP's web-based Registration and Credential Repository (RCR) (<https://ctepcore.nci.nih.gov/rcr>). Documentation requirements per registration type are outlined in the table below.

Documentation Required	IVR	NPIVR	AP	A
FDA Form 1572	✓	✓		
Financial Disclosure Form	✓	✓	✓	
NCI Biosketch (education, training, employment, license, and certification)	✓	✓	✓	
HSP/GCP training	✓	✓	✓	
Agent Shipment Form (if applicable)	✓			
CV (optional)	✓	✓	✓	

An active CTEP-IAM user account and appropriate RCR registration is required to access all CTEP and CTSU (Cancer Trials Support Unit) websites and applications. In addition, IVRs and NPIVRs must list all clinical practice sites and IRBs covering their practice sites on the FDA Form 1572 in RCR to allow the following:

- Added to a site roster
- Assigned the treating, credit, consenting, or drug shipment (IVR only) tasks in OPEN
- Act as the site-protocol PI on the IRB approval
- Assigned the Clinical Investigator (CI) role on the Delegation of Tasks Log (DTL).

Additional information can be found on the CTEP website at <https://ctep.cancer.gov/investigatorResources/default.htm>.

For questions, please contact the RCR **Help Desk** by email at [[contact]](mailto:[contact])

##### CTSU Registration Procedures

This study is supported by the NCI Cancer Trials Support Unit (CTSU).

##### IRB Approval:

Each investigator or group of investigators at a clinical site must obtain IRB approval for this protocol and submit IRB approval and supporting documentation to the CTSU Regulatory Office before they can be approved to enroll patients. Assignment of site registration status in the CTSU Regulatory Support System (RSS) uses extensive data to make a determination of whether a site has fulfilled all regulatory criteria including but not limited to the following:

- An active Federal Wide Assurance (FWA) number
- An active roster affiliation with the Lead Network or a participating organization
- A valid IRB approval
- Compliance with all protocol specific requirements.

In addition, the site-protocol Principal Investigator (PI) must meet the following criteria:

- Active registration status
- The IRB number of the site IRB of record listed on their Form FDA 1572
- An active status on a participating roster at the registering site.

Sites participating on the NCI CIRB initiative that are approved by the CIRB for this study are not required to submit IRB approval documentation to the CTSU Regulatory Office. For sites using the CIRB, IRB approval information is received from the CIRB and applied to the RSS in an automated process. Signatory Institutions must submit a Study Specific Worksheet for Local Context (SSW) to the CIRB via IRBManager to indicate their intent to open the study locally. The CIRB's approval of the SSW is then communicated to the CTSU Regulatory Office. In order for the SSW approval to be processed, the Signatory Institution must inform the CTSU which CIRB-approved institutions aligned with the Signatory Institution are participating in the study.

#### **Downloading Site Registration Documents:**

Site registration forms may be downloaded from the **E2112** protocol page located on the CTSU members' website.

- Go to <https://www.ctsu.org> and log in to the members' area using your CTEP-IAM username and password
- Click on the Protocols tab in the upper left of your screen
- Either enter the protocol # in the search field at the top of the protocol tree, or
- Click on the By Lead Organization folder to expand
- Click on the ECOG-ACRIN link to expand, then select trial protocol E2112
- Click on LPO Documents, select the Site Registration documents link, and download and complete the forms provided.

Rev. 10/16

